APPENDIX 11– SAE REPORT FORM

SEVERE ADVERSE EVENT (SAE) REPORT FORM

STUDY TITLE	Low dose aspirin for preventing intrauterine growth restriction and preeclampsia in sickle cell pregnancy (PIPSICKLE): a randomised controlled trial.		
Site No.			
SITE Name			
PATIENT ID		DATE OF REPORT	dd-mm-yyyy

1.	SAE Date of Onset:	dd-mm-yyyy
2.	SAE Date Stopped:	dd-mm-yyyy
3.	Location of SAE:	
4.	Was this an unexpected adverse event?	 Yes  No
5.	Brief description of participants (do not include personal identifiers):	Age
		Diagnosis for study participation
6.	Brief description of the nature of the SAE: attach description, if applicable	
7.	Category of SAE:	 Date of Death: dd-mm-yyyy  Life threatening  Congenital anomaly, birth defects  Life threatening  Required intervention to prevent impairment (permanent)  Hospitalization  Disability

		 Other:
8.	Describe study intervention	
9.	Relationship of event to intervention:	 Unrelated  Possible  Definite
10.	Was the study intervention discontinued due to the event?	 Yes  No
11.	What steps were taken to treat the SAE?	
12.	List relevant tests, lab data, history, and pre-existing medical conditions:	
13.	Report type:	 Initial  Follow-up  Final

Print Name of Site Investigator

Signature of Principal Investigator

Date

Print Name of Principal Investigator

Signature of Principal Investigator

Date

APPENDIX 12 – STUDY MONITORING LOG

PIPSICKLE TRIAL STUDY INITIATION CHECKLIST

STUDY TITLE	Low dose aspirin for preventing intrauterine growth restriction and preeclampsia in sickle cell pregnancy (PIPSICKLE): a randomised controlled trial.
SITE NAME ; CODE	
SITE INVESTIGATOR	
MONITOR NAME	
DATE OF VISIT	
METHOD OF VISIT	 On-Site  Teleconference  Other, specify:

List personnel in attendance from site, below. Attach attendance sheet.

NAME, TITLE	ROLE

Verify each document or activity required below. Attach any supporting documentation.

NO.	DOCUMENT OR ACTIVITY (DISCUSSED/VERIFIED)	YES	NO	N/A	COMMENTS
1	Staff CVs signed/dated				
2	Staff trained on protocol				
3	Staff read investigator brochure for product				
4	Check required number of forms delivered to site (i.e. consent forms, case forms).				
5	PI and site have agreed to study contract and budget.				
6	HREC/IRB approval granted/renewed for study.				
7	Staffing allocation complete.				
8	Specific staff responsibilities discussed with staff				
9	Required facilities are available/functional.				
10	Study drugs stored appropriately.				
11	Materials/equipment for study available/received.				
12	Materials/equipment for study stored and maintained appropriately				
13	Investigator's file prepared and maintained				
14	Final contract and budget signed and filed.				
15	e-case forms available (if applicable)				
16	Drug shipment received (if applicable)				

CONFIDENTIAL

NO.	DOCUMENT OR ACTIVITY (DISCUSSED/VERIFIED)	YES	NO	N/A	COMMENTS
17	Other supplies received (if applicable)				

Name of Monitor (Print)

*Monitor Signature**Date*

Name of Principal Investigator (Print)

*Principal Investigator Signature**Date*

CONFIDENTIAL

[Version 4]

[21st MAY 2024]

[PIPSICKLE]

Page 118 of 121

PROTOCOL DEVIATION TRACKING LOG

CONFIDENTIAL

CONFIDENTIAL

1.1 Preface

Nigeria has the highest number of people living with sickle cell disease (SCD) in the world, amounting to 2-3% of the population(1). Sickle cell disease is a hemoglobinopathy fraught with complications because of vaso-occlusion, thrombosis, and chronic anemia. The red blood cells become abnormal and fragile when deoxygenated, forming polymers and adhering to vascular endothelial tissue with resultant obstruction of the vessels and hemolysis(2,3). These lead to various clinical manifestations, which include splenic sequestration, susceptibility to infections, stroke, bone pain crises, and acute chest syndrome(4). Vasoconstriction from nitric oxide depletion has also been postulated to be a pathophysiological mechanism for some of its adverse effects such as pulmonary hypertension and stroke(5).

Over 50% of females with SCD now achieve pregnancy due to increased survival into adulthood, but they have a high incidence of complications during pregnancy, including preeclampsia (PE) and intrauterine growth restriction (IUGR), infections, acute chest syndrome, and more frequent crises(6–8). Many pregnant women with sickle cell disease are thus more likely to die in pregnancy, especially in low-resource settings like ours(6); pregnancy-related studies in them should, therefore, be a priority. Even when they do not die, a large proportion of pregnant sickle cell patients develop morbidities that can be defined as “maternal near miss,” meaning they would have died but for prompt and appropriate intervention(9).

Previously, we found a reversal in a prostacyclin-thromboxane ratio in pregnant hemoglobin (Hb) SS women(10), a situation that is also found in non-sickle pregnancies with preeclampsia and unexplained IUGR(11). Low-dose aspirin (LDA) has been shown to reduce the incidence of PE and IUGR in high-risk women due to its reduction of vasoconstrictor thromboxane whilst sparing prostacyclin, in effect correcting the ratio(12). It has been found to be safe for use in pregnancy (13) and has been suggested for use in sickle cell pregnant women(14), but all the studies were conducted in non-SCD pregnant women. To the best of our knowledge, there are no studies evaluating the role of low-dose aspirin in the prevention of preeclampsia and IUGR in pregnant SCD women in the scientific literature(15). As women with SCD have such a high incidence of morbidity and mortality in pregnancy, the results of this study could potentially save their lives and that of their babies.

1.2 Scope of the analyses

To determine whether daily administration of 100mg LDA from 12 - 28 weeks of gestation till 36 weeks reduces the risk of IUGR, preeclampsia, perinatal deaths or miscarriages, and other complications (sickling and non-sickling related) in pregnant HbSS women compared with the use of placebo.

2 Study Objectives and Endpoints

2.1 Study Objectives

- 1) To determine the effect of the use of LDA during pregnancy in Hb SS and Hb SC women on the risk of intrauterine growth restriction (IUGR), perinatal death, or miscarriage (composite outcome).
- 2) To determine the effect of the use of LDA during pregnancy in Hb SS and Hb SC women on the risk of other maternal complications, including preeclampsia, preterm delivery, number of vaso-occlusive crises, need for blood transfusion, urinary tract infections, respiratory tract infections, acute chest syndrome, retained placenta, placental abruption, and vaginal bleeding.

2.2 Endpoints

Primary

1. IUGR, perinatal death or miscarriage as a composite outcome

The occurrence of either IUGR, perinatal death or miscarriage will be the primary outcome.

IUGR will be defined as birthweight <10th centile for gestational age on the INTERGROWTH-21st birthweight charts, which is based on a healthy reference cohort from multiple countries, including Kenya(16). IUGR based on the Oken charts from a US national reference(17) maybe presented in sensitivity. A perinatal death refers to the death of a fetus after the age of viability (≥ 28 weeks' EGA), at delivery, or within the first week of life. A miscarriage refers to pregnancy, loss the death of a fetus before the age of viability (< 28 weeks' EGA). All participants will do an ultrasound scan at 20 weeks to estimate the gestational age of the pregnancy. Analysis will be by intention to treat.

Hypothesis:

1. We expect a 50% lower incidence of IUGR, perinatal death or miscarriage in the LDA (intervention) group compared to the placebo (control) group.

Secondary

1. The incidence of preeclampsia. Preeclampsia will be diagnosed based on ISSHP classification(18) if there is development of hypertension (either systolic blood pressure ≥ 140 mm Hg or diastolic blood pressure ≥ 90 mm Hg on two occasions at least 4 h apart) after 20 weeks gestation plus one of the following: proteinuria, thrombocytopenia, or any multisystem complication. Proteinuria will be defined as a dipstick test with 1+ proteinuria (≥ 30 mg dl $^{-1}$) on two occasions at least 4 hours apart, without any evidence of a urinary tract infection, or 2+ proteinuria or more on dipstick, or urinary protein creatinine ration >300 mg/g. Thrombocytopenia will be defined as a platelet count of $<100,000$ mm $^{-3}$.
2. The incidence of preterm delivery, defined as delivery at <37 weeks' EGA.
3. The incidence of:
 - a. Maternal death
 - b. Perinatal death
4. Number of sickle cell crises
5. Need for blood transfusion – identified based on whether the participant received a blood transfusion or not
6. Incidence of complications such as:
 - a. Urinary tract infection (UTI),
 - b. Lower Respiratory Tract Infection,
 - c. Acute chest syndrome,
 - d. retained placenta,
 - e. placental abruption; and
7. Incidence of potential adverse effects such as:
 - a. vaginal bleeding,
 - b. epigastric pain, and
 - c. heartburn

Analysis will be by intention to treat.

3 Study Methods

3.1 General Study Design and Plan

[figure not shown]
A multicenter clinical trial with a double-blind parallel design, with 476 women allocated in a 1:1 ratio.

Daily administration of 100 mg aspirin tablet. Oral route.

Daily administration of placebo similar in appearance to the aspirin tablet. Oral route.

Participants will be seen in clinic every 4 weeks till 28 weeks' gestation and every 2 weeks until 36 weeks, then weekly until delivery.

Figure 1. Flowchart of participant selection

3.2 Inclusion-Exclusion Criteria and General Study Population

Inclusion criteria

- Age 18 years and above
- Singleton foetus
- Women whose genotypes are haemoglobin SS or SC.
- 12 – 28 weeks gestation recruitment, estimated from the last menstrual period or by an early ultrasound scan done before 22 weeks gestation.

Exclusion criteria

- Women with associated medical conditions in pregnancy e.g., HIV infection, diabetes mellitus, hypertension, renal disease, sickle nephropathy
- Hb genotype other than HBSS or HbSC
- Hypersensitivity to aspirin
- A vaso-occlusive crisis in the last 4 weeks

- History of blood transfusion in the last 3 months
- Women who participated in the PIPSICKLE trial during their previous pregnancy

3.3 Randomization and Blinding

At the enrolment visit, any pregnant woman with haemoglobin SS or SC, who meets the eligibility criteria and gives informed consent will be enrolled. Eligible participants will be consecutively enrolled. They will be randomized to one of the two treatment groups. Individual randomization and allocation concealment will be done with the use of a web-based randomization software known as 'Sealed envelope' in a 1:1 ratio in blocks of four. Sealed envelope generated a randomisation code list, shared only with the unblinded pharmacist by email. Each code is pasted on the appropriate drug kit and the drug kits are sent out to each site by the unblinded pharmacist, who is not in contact with any of the site investigators.

Preterm delivery	Continuous variable, measured in weeks. The lower limit of acceptable range is 12 weeks. The usual upper limit is 44 weeks, beyond which baby is unlikely to have survived. 
 ▪ A secondary endpoint
Maternal mortality	Binary variable (0, 1). Defined as any death of a woman during the study (during pregnancy and puerperium) 
 ▪ A secondary endpoint
Haemoglobin F	Categorical variable (<2%, 2 – 10%, >10%), measured in percent. Calculated

Variable	Description
fraction	from continuous HbF fraction 
 ▪ A baseline covariate ▪ Levels of HbF fraction are related to clinical outcomes among people with sickle cell disease(19)
Haemoglobin A2 fraction	Categorical variable (<3.5%, ≥3.5%), measured in percent. Calculated from continuous Hb A2 fraction 
 ▪ A baseline covariate ▪ Levels of HbA2 fraction are suggestive of β thalassemia carrier status(20)
Follow-up duration	Continuous variable, measured in days. Calculated as the difference between the date of randomization to the date of delivery or miscarriage.

4 Sample Size

Assuming an incidence of intrauterine growth restriction (IUGR) of 20% in sickle cell disease(21) and expecting a 50% IUGR reduction with the use of LDA as detected by Bujold et al(22), we calculated that 198 women per group would be required to have a 90% power of detecting a decrease in IUGR at the 5% significance level, with a total of 396, using the formula for proportions in superiority parallel trial(23). Allowing for 20% attrition, this would become 476 in total.

5 General Analysis Considerations

5.1 Timing of Analyses

The final analysis will be performed on the final unblinded dataset, after data cleaning is completed and database is locked.

5.2 Analysis Populations

5.2.1 Intention to Treat (ITT) population

- The intention to treat population refers to all subjects who were randomised. Following the intention-to-treat principle, patients will be analysed according to the treatment they were assigned to at randomization.

5.3 Covariates and Subgroups

The following table is a list of covariates to be presented in Table 1, and to be explored for inclusion in models.

Table shell 1. Participant characteristics

Variables	LDA	Placebo	Overall
Age			
Mean (SD)			
Median [IQR]			
Age Categories (years)			
<20			
20 - <30			
30 - <40			
40 and above			
Haemoglobin genotype			
Hb SC			
Hb SS			
Fetal hemoglobin fraction			
<2%			
2 – 10%			
>10%			
Hemoglobin A2 fraction			
<3.5%			
≥3.5%			
Hemoglobin concentration			
Mean (SD)			
Median [IQR]			
Primip			
Yes			
No			
Gestational age at enrollment			
Mean (SD)			
Median [IQR]			
Body weight			
Mean (SD)			
Median [IQR]			
Educational_attainment			

Variables	LDA	Placebo	Overall
No formal education			
Completed Primary			
Completed Secondary			
Completed Tertiary			
Currently in School			
Postgraduate			
Married			
No			
Yes			

Values are n(%) for categorical variables and mean (SD) or median (min, max) for continuous variables. The decision to report the mean (SD) or median (min, max) may be guided by the distribution of the variable based on the Shapiro-Wilk test

5.4 Missing Data

No imputation of endpoints will be done in the main analysis. Throughout, the denominator for each analysis will be reported to be transparent wherever there is missing data. For outcomes missing in <5% of those for whom it is expected, missing data will be ignored as imputation is unlikely to improve the precision or prevent bias(24). This approach is known as a *complete-case intention-to-treat* approach(25).

For outcomes missing in ≥5% of participants for whom it is expected, supplementary tables comparing baseline characteristics in those with and without the missing outcome will be reported. In addition, multiple imputation or inverse probability of treatment weighting will be considered, and results compared with the complete case analysis.

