5.5 Multiple Testing

There is one primary endpoint in our analysis, and no adjustment for multiple testing will be done(26). Thus, our analysis's alpha level for statistical inference will be 0.05, and all p-values will be presented to the third decimal place.

6 Summary of Study Data

Baseline covariates will be summarized and stratified by intervention arm to describe the population . Continuous variables will be summarized using the following descriptive statistics, n (non-missing sample size), mean, standard deviation (SD), medians, interquartile ranges (IQR), minimum and maximum. The frequency and percentages (based on the non-missing sample size) of observed levels will be reported for all categorical measures. In general, all summary tables will be structured with a column for the overall population. Summary tables will also be presented for each treatment and will be annotated with the total population size relevant to that table/treatment. The number of missing observations will be presented in the footnote of each table.

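### SAP 5.4 offers inverse probability of treatment weighting for missing outcomes; it models arm assignment, not missingness, so its agreement with the complete-case result would not show that loss is harmless

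*SAP*

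**What the plan says.** SAP 5.4 makes the main analysis complete-case: "No imputation of endpoints will be done in the main analysis". Denominators are to be reported throughout, and missing data are ignored when under 5% of an outcome is missing. At 5% or more, two things follow. Tables comparing baseline characteristics of women with and without the outcome will be reported. In addition, "multiple imputation or inverse probability of treatment weighting will be considered, and results compared with the complete case analysis".

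The SAP does not say which of the two methods will be used, what the weight model contains, or on whom it is fitted. It names no weighting for missingness or censoring and no missing-not-at-random analysis. Protocol 9.3 is silent on missing outcomes.

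Three other statements matter. Allocation is 1:1 (SAP 3.1 and 3.3). The intention-to-treat population is all randomised women (SAP 5.2.1). The sample size carries a loss allowance: "Allowing for 20% attrition, this would become 476 in total" (SAP section 4).

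**The concern.** A missing-data check is useful only if it can give a different answer when loss is selective. Treatment weighting uses the probability of receiving the assigned arm. In a randomised trial that probability is known and has nothing to do with whether the outcome was recorded. If this option is chosen and its result sits beside the complete-case result, close agreement may be read as robustness when the method had little or no ability to disagree. The primary composite is analysed complete-case, so such a check would be one of the few guards against selective loss in the main result.

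**Working it through.** **1. Would the 5% branch be reached?** The plan's own figure reproduces: 198 × 2 = 396, and 396 × 1.2 = 475.2, rounded up to 476. That leaves room to lose 476 − 396 = 80 women, or 80/476 = 16.8%. The trigger needs 0.05 × 476 = 23.8, so 24 women. The allowance is well above the trigger, but it is a planning margin and not a forecast of missing primary outcomes.

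**2. What the weights do.** With e = P(aspirin) = 0.5, the weights are 1/e = 2 and 1/(1 − e) = 2. In each arm the weighted risk is Σ2Y/Σ2 = ΣY/n, the complete-case risk. With covariates in the model, the weights move only for chance imbalance at randomisation.

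**3. Worked example.** The rates below are assumptions; the documents give none of them. 70% of women are HbSS (risk 25% placebo, 12.5% aspirin) and 30% HbSC (10% in both arms). The outcome is observed in 70% of HbSS and 95% of HbSC women on placebo, and in 85% and 75% on aspirin.

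- True: placebo 0.7 × 0.25 + 0.3 × 0.10 = 0.205; aspirin 0.7 × 0.125 + 0.3 × 0.10 = 0.1175; RR 0.573.
- Complete-case: placebo (0.49 × 0.25 + 0.285 × 0.10)/0.775 = 0.1948; aspirin (0.595 × 0.125 + 0.225 × 0.10)/0.82 = 0.1181; RR 0.606. Missing: 22.5% and 18%, mean 20.25%.
- Treatment weighting, all randomised: 0.606, by step 2.
- Treatment weighting, completers: both arms take the completers' genotype mix, HbSS share (0.49 + 0.595)/(0.775 + 0.82) = 0.680. Placebo 0.2020, aspirin 0.1170, RR 0.579.
- Missingness weighting (1/probability observed, by arm and genotype) restores 70/30 in each arm: RR 0.573.

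If the 70%/95% pattern holds in both arms (22.5% missing), the HbSS share among completers is 0.49/0.775 = 0.632 in each arm. The risks are 0.1948 and 0.1158, RR 0.594. Both forms of treatment weighting also give 0.594.

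**4. Other patterns of loss.** These are also assumptions. Rows A to C and E use a baseline factor X present in half the women, with placebo risk 30% or 10%.

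- A and B: loss is 50% for aspirin women with X and 10% otherwise (30% v 10% by arm).
- C: loss is 35% with X and 5% without in both arms; RR is 0.75 with X and 0.25 without.
- D: 238 per arm; risk 28% or 12% by X; a recorded post-baseline factor is present in 60% of women with the outcome and 15% without. With the factor, loss is 65% on aspirin and 20% on placebo; without it, 8%.
- E: loss is 50% for aspirin women with the outcome and 13% otherwise.

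| Pattern | True RR | Complete case | Treatment wt, all randomised | Treatment wt, completers | Missingness wt |
|---|---|---|---|---|---|
| A. X and arm, no effect | 1.00 | 0.86 | 0.86 | 1.00 | 1.00 |
| B. As A, constant effect | 0.50 | 0.43 | 0.43 | 0.50 | 0.50 |
| C. X, effect differs by X | 0.62 | 0.58 | 0.58 | 0.58 | 0.62 |
| D. Post-baseline factor, no effect | 1.00 | 0.77 | 0.77 | 0.78 | 0.78 baseline only; 1.00 with the factor |
| E. Unseen outcome, no effect | 1.00 | 0.63 | 0.63 | 0.64 | 0.64 |

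The table is simulated. Closed form agrees: in A the complete-case aspirin risk is (0.25 × 0.30 + 0.45 × 0.10)/0.70 = 0.171 against 0.20, RR 0.86. In C the exact values are 0.125/0.20 = 0.625 and 0.10625/0.18125 = 0.586.

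Treatment weighting on all randomised women matched the complete-case value in every row. On completers it worked in A and B and failed in C, D and E.

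**5. Size against sampling error.** In step 3 the bias is ln(0.606/0.573) = 0.056. With 238 × 0.775 = 184 and 238 × 0.82 = 195 completers, the standard error of the log risk ratio is about 0.25, so the bias is under a quarter of a standard error and toward the null. In the equal-loss version it is about 0.14 standard errors. In A it is ln(0.86) = −0.15, away from the null.

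**The case against.** A reader might infer that the missing-data check will agree with the complete-case result by construction, so that biased loss will be reported as harmless. The documents do not support that.

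- Multiple imputation is named first, and it does model the missing outcome. Both methods are only to be considered, so no treatment-weighted check is firmly planned.
- Near-exact agreement is guaranteed only if the weights are fitted on all randomised women, which the SAP does not specify. Fitted on completers, the step 3 estimate moves from 0.606 to 0.579, removing 0.027 of the 0.033 error (about 80%), and in A and B the error disappears.
- At 5% or more missing, baseline tables of women with and without the outcome are required. SAP section 9 repeats the primary analysis by genotype if each subgroup has at least 30 women, and SAP 7.1 allows covariate adjustment. Loss related to genotype would probably be noticed.
- The step 3 bias is small, and its first pattern needs loss to run in opposite directions by genotype across arms.
- Missingness weighting on baseline variables alone does no better in D, and no such weighting repairs E.
- The 5% trigger may not be met. Protocol 7.7 follows women who stop study drug, whereas Protocol 6.1 lists stopping it as a reason for mandatory withdrawal. The two must be reconciled, since they affect how many outcomes go missing and whether loss relates to arm.

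All of this stands and limits the consequence. It does not rescue the named method. The SAP gives no rule for choosing between the options, so the uninformative one could be picked after the data are seen. The term may be a slip for censoring weighting, but nothing in the documents shows that, and a programmer working from the SAP would implement what is written.

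**Conclusion.** The treatment-weighting option in SAP 5.4 is the wrong tool for missing outcomes. If it is used, agreement with the complete-case result is not evidence that loss is harmless. That conclusion follows from 1:1 allocation and needs no assumed rates.

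The size of any bias left undetected does rest on assumptions. It runs from a risk ratio of 0.594 or 0.606 against a true 0.573 in the genotype examples to 0.77 against 1.00 when a post-baseline factor drives loss. Outcome-dependent loss gives 0.63 against 1.00, but neither missingness weighting nor imputation under missing-at-random repairs that.

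The defect affects one of two optional methods, conditional on a trigger that is plausible but not certain to be met. It should be corrected before unblinding; it does not invalidate the primary analysis.

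**What to change.** In SAP 5.4:

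1. Replace inverse probability of treatment weighting with inverse probability of missingness (censoring) weighting. Model whether the outcome was observed on arm, baseline predictors (genotype, gestational age at enrolment, and site) and recorded post-baseline predictors of loss. With 15 sites and about 32 women per site (476/15), enter site in a form that keeps the weights stable, such as grouped sites. Post-baseline variables belong in the missingness and imputation models only, not as adjustment covariates in the outcome model.
2. For the primary composite at 5% or more missing, commit to multiple imputation by arm using the same variables, with missingness weighting as the check, in place of leaving both to be considered.
3. Add a simple delta or tipping-point analysis for missing-not-at-random loss, since neither method above repairs it.

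The cost is an SAP wording change and a little more analysis and programming. No new data are needed, and the complete-case main analysis is unchanged.
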